**Table 2: Aims, Hypotheses, and Associated Measures**

*Pre-bereavement measures collected at baseline, 14, 30, 90, and 150 days (follow-up data collection post 150 days will occur every 6 weeks until participant transitions to bereavement). Post-death measures collected at transition, 14, 30, 90, 150 and 180 days. During study wind down, participants will complete their final data collection measure based on where they are at in the intervention (e.g., if a participant is on day 90 of 150, they will complete day 90 survey as their final measure).*

Specific Aim	Hypotheses (H) and Research Questions (RQ)	Instruments and Variables	Description
Aim 1: Determine the efficacy of the Caregiver Speaks intervention in reducing depression and anxiety among hospice family caregivers of PLWD.	RQ1: What is the effect of the Caregiver Speaks intervention on caregivers' depression, anxiety (outcomes of interest)? H1a: Family caregivers receiving the intervention will	Primary Outcome: Depression Patient Health Questionnaire (PHQ-9) Secondary Outcome: Anxiety Generalized	PHQ-9: a 9-item screening tool and severity measure for depressive mood.  Internal Consistency: .87 

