### **Data Analysis Plan:**

**Statistical Assumptions.** We will examine linearity and homoskedasticity by calculating and plotting residuals and Cook's distance for all models. Where data are missing, we will use the Last Observation Carried Forward (LOCF) missing data imputation technique, given that < 30% of data were missing for any particular subject in our prior work. If the proportion of missing data is higher, we will use regression based multiple imputation. Little's MCAR test (missing completely at random) will be used to test that missingness is in no way related to the intervention. Because the sample size is relatively large, we expect that known and unknown confounders will be distributed evenly among the two randomized groups. Additional confounders will only be introduced as covariates if we find evidence of imbalance between groups at baseline. We acknowledge that this study is not powered to detect small interaction effects.

We will test whether randomization created balanced groups by comparing baseline measures and demographic characteristics, using chi-square or t-test analysis for categorical or continuous variables, respectively. Variables that differ significantly between groups will be included in regression models as potential confounders. We will include time from study enrollment to the last observation as a covariate, as well as hospice agency. We will report estimates with 95% confidence intervals. To draw inferences from our study for the likely benefit to an equivalent population, where the intervention under trial is a model of service delivery, all analyses of outcomes will be by intention-to-treat. The intention-to-treat analysis, consistent with the objectives of a pragmatic trial, will minimize the influence of "informative missingness" of the data and preserve groups' comparability.

**Statistical Analysis.** H1a: Family caregivers receiving the intervention will report lower levels of depression and anxiety (outcomes of interest), which is facilitated by higher social support (mediating variable) than those in the control group during active caregiving.

H1b: Family caregivers receiving the intervention will report lower levels of depression and anxiety (outcomes of interest), which is facilitated by higher social support (mediating variable) than those in the control group during bereavement.

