### **IX. Compensation**

Subjects will be compensated \$100 total. One payment of \$50 will be made via a check at the transition period, and the second \$50 payment after completion of their exit interview. During study wind down, all participants will receive their final payment on or around the time of their final survey. Meaning, if participants are on day 90 of 150 and they complete day 90 as their final survey, investigators will initiate final payment. All participants will receive the total amount of their compensation (\$100) at the completion of their final survey, regardless of whether they have entered the bereavement phase.

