# **Caregiver Speaks Data Analysis Plan**

**January 5, 2019**

**NCT04103580**

## Data Analysis

### Statistical Assumptions

We will routinely test assumptions of linearity, independence and homoskedasticity by calculating and plotting residuals and Cook's distance for all models. Where data are missing, we will substitute the mode for categorical data and the median for continuous data, given that <0.5% of data were missing for any measure in our preliminary trial. If the proportion of missing data is higher, we will use multiple imputation. In the analysis for H1a, we will use the final measure provided by caregiver before patient death, and for H1b we will use the final measure during bereavement. Because the sample size is relatively large, we expect that known and unknown confounders will be distributed evenly among the two groups. We acknowledge that this study is not powered to detect small interaction effects. Additional confounders will only be introduced as covariates if we find evidence of imbalance between groups at baseline.

We will test whether randomization created balanced groups by comparing baseline measures and demographic characteristics, using chi-square or t-test analysis for categorical or continuous variables, respectively. Variables that differ significantly between groups will be included in regression models as potential confounders. To compare outcomes for our hypotheses, we will use the last available measure post-baseline and prior to death or the end of the study and last measure during bereavement. This is a last-observation analysis.

Carpenter and Kenward argue that, in such analyses, time to this event should be taken into account. Therefore, we will include time from study enrollment to the last observation as a covariate. We will report estimates with 95% confidence intervals. To draw inferences from our study to the likely benefit to an equivalent population where the intervention under trial is a model of service delivery, all analyses of outcomes will be by intention-to-treat. The intention-to-treat analysis, consistent with the objectives of a pragmatic trial, will minimize the influence of "informative missingness" of the data and preserve groups' comparability.

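### The protocol's LOCF rule does not stop at the patient's death, so caregiving PHQ-9 or GAD-7 scores can be carried into bereavement time points used for H1b

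*Protocol*

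**What the plan says.** **Protocol, Data Analysis Plan, Statistical Assumptions.** The rule is "Where data are missing, we will use the Last Observation Carried Forward (LOCF) missing data imputation technique". The reason follows, "given that < 30% of data were missing for any particular subject in our prior work", and then a fallback: "If the proportion of missing data is higher, we will use regression based multiple imputation". No sentence limits the carry-forward to one phase of the study. The reason is worded per subject, but the fallback speaks only of a proportion and does not say of what.

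**Protocol, Table 2.** PHQ-9 and GAD-7 serve both H1a (active caregiving) and H1b (bereavement). Pre-death surveys fall at baseline and at 14, 30, 90 and 150 days, then every six weeks. After that: "Post-death measures collected at transition, 14, 30, 90, 150 and 180 days".

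**Protocol, Statistical Analysis.** The outcomes are analysed with a linear mixed model that has one time variable and one slope per arm. The text notes that such models cope with unequal numbers of measurements. The model has no term for phase.

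**SAP, Statistical Assumptions.** The two phases are separated at the death. For the first: "In the analysis for H1a, we will use the final measure provided by caregiver before patient death". For the second: "for H1b we will use the final measure during bereavement". The SAP's own rule for missing data is the mode or median, with multiple imputation if more is missing. It has no LOCF imputation rule.

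**The concern.** H1b asks whether the intervention lowers depression and anxiety after the death. A score given while the patient was alive does not measure that. Because the same two instruments run through both phases, the last observation before a missed bereavement survey may be a caregiving score, and nothing in the LOCF sentence prevents its use.

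Three consequences follow wherever this happens:

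- A benefit confined to active caregiving would appear in part as a bereavement benefit.
- A benefit confined to bereavement would be diluted.
- If the arms differ in how often scores are carried across, any ordinary shift in PHQ-9 at the death would become an arm difference with no treatment effect behind it.

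PHQ-9 is the primary outcome, and H1b is one of its two between-arm hypotheses. H2 is not exposed in the same way: the grief scale is described for bereaved people and so should have no pre-death value to carry.

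**Working it through.** No sample size or power figure in the documents depends on this rule, so there is no stated figure to reproduce. The check is whether the 30% condition already prevents a carry across the death, and what a carry would do if it does not.

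**Inputs from the documents:** the Table 2 schedule (five fixed pre-death surveys, then one every 42 days; six bereavement surveys) and the 30% condition. **Not given:** the share of scores carried across (f), the effect in each phase, and the change in score at the death.

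**Step 1. Per-caregiver reading, no bereavement survey at all.** With k completed pre-death surveys, the missing share is 6/(6 + k).

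| k | Day of last pre-death survey | Missing share |
|---|---|---|
| 1 | 0 | 6/7 = 86% |
| 3 | 30 | 6/9 = 67% |
| 5 | 150 | 6/11 = 55% |
| 14 | 150 + 9 × 42 = 528 | 6/20 = 30.0% |
| 15 | 150 + 10 × 42 = 570 | 6/21 = 28.6% |

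Such a caregiver falls below 30% only after about 570 days of pre-death surveys. Before that the rule sends them to multiple imputation.

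**Step 2. Per-caregiver reading, early bereavement surveys missed.** With m missed, the share is m/(6 + k).

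- Five pre-death surveys; transition, day 14 and day 30 missed: 3/11 = 27%.
- Baseline only; transition and day 14 missed: 2/7 = 28.6%.

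Both are below 30%, so LOCF applies and the carried value is a pre-death score. If only surveys already due at study wind-down are counted (an assumption; the protocol does not say), a caregiver with five pre-death surveys and only transition and day 14 due, both missed, is also at 2/7 = 28.6%, with no bereavement data at all.

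**Step 3. Trial-wide reading.** If overall missingness is below 30%, no per-caregiver limit applies. Any bereaved caregiver with no post-death survey can then have the last caregiving score placed at all six bereavement time points. The protocol assumes 30% attrition but does not say when it occurs, so which side of the limit the trial would fall on cannot be told.

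**Step 4. Size at a bereavement time point.** Suppose the same share f is carried in each arm, and effects are alike in carried and observed caregivers. Then

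estimate ≈ (1 − f) × bereavement effect + f × pre-death effect.

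| Bereavement effect | Pre-death effect | f = 10% | f = 20% | f = 30% |
|---|---|---|---|---|
| −4 | 0 | −3.6 | −3.2 | −2.8 |
| −4 | −2 | −3.8 | −3.6 | −3.4 |
| −2 | 0 | −1.8 | −1.6 | −1.4 |
| 0 | −2 | −0.2 | −0.4 | −0.6 |

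**Step 5. Unequal shares, no effect in either phase.** If scores change by D on average at the death, the spurious difference (intervention minus control) is (f control − f intervention) × D. With 20% in control and 30% in intervention, D = +1 gives −0.1, D = +3 gives −0.3 and D = −3 gives +0.3.

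Steps 4 and 5 describe a difference in mean scores at one time point. The protocol's model compares slopes. There the distortion depends on which time points are filled, and it was not computed.

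**The case against.** The strongest reply is that LOCF is conditional. Take a caregiver who completes baseline, day 14 and day 30, whose patient dies on day 60, and who then answers nothing. That caregiver has 6 of 9 surveys missing (67%). Read per caregiver, the protocol sends this person to multiple imputation and carries nothing forward. This stands. A reader might infer that every caregiver without a bereavement survey is simply assigned a caregiving score for H1b. No sentence says so, and on the per-caregiver reading it would almost never happen. The reply does not cover the early-missed surveys of Step 2, or the trial-wide reading. The SAP's parallel sentence justifies its rule by missingness per measure, so a per-caregiver limit cannot be taken for granted.

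Second, the SAP already defines H1b by a measure taken in bereavement, and its own imputation rule is not LOCF. This also stands, and it shows what H1b is meant to measure. But the SAP is dated January 2019, while the protocol records changes from 2021 and 2022, and neither says which rule for missing data governs. A caregiver who misses only early bereavement surveys also still has an observed final measure, so a last-observation analysis as in the SAP would be unaffected in that case. The exposure there is in the protocol's repeated-measures model.

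Third, the mixed model does not need filled values. True, but the protocol orders filling anyway, and filled values would enter the model as bereavement data.

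A reader might also infer that caregivers whose patient is alive at wind-down are filled in for H1b, because analysis is by intention-to-treat and the Compensation section pays participants "regardless of whether they have entered the bereavement phase". The documents do not support this. That sentence is a payment rule, post-death surveys were never due for these caregivers and so are not missing, and intention-to-treat concerns the assigned arm.

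**Conclusion.** The point holds as a gap in the rule. The protocol permits a caregiving PHQ-9 or GAD-7 score to stand in for a bereavement score, and such a value conflicts with the SAP's definition of the H1b outcome. The documents do not show that this will happen to most, or to any given number, of caregivers.

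How far it reaches depends on the unstated scope of the 30% condition: caregivers who miss early bereavement surveys if it is per caregiver, or any bereaved caregiver with no post-death score if it is trial-wide and overall missingness stays below 30%. Where it occurs, the mean difference at a bereavement time point moves toward the pre-death effect by the fraction f. In the illustrations, 10% to 30% carried turns a 4-point bereavement-only benefit into 3.6 to 2.8 points, and a 2-point caregiving-only benefit into an apparent 0.2 to 0.6 points in bereavement. These sizes rest on assumed shares and effects, equal loss in the arms, and a simpler comparison than the planned model. The gap is worth closing before analysis because doing so costs almost nothing.

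**What to change.** In the protocol's Statistical Assumptions, and in matching words in the SAP:

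- State that no PHQ-9 or GAD-7 value is carried across the patient's death, and that H1b uses as outcomes only scores collected after it.
- State that missing bereavement scores are handled by the planned mixed model on observed data. Where a filled value is needed, use the regression-based multiple imputation already planned, run by arm, with baseline and pre-death scores as predictors and not as substitutes.
- Say whether the 30% condition is per caregiver or trial-wide, and which document's rule for missing data governs.
- Report, by arm, how many bereaved caregivers have no post-death score.

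This is a change of wording and needs no new data. The cost is fewer filled values and a slightly wider confidence interval for H1b.

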### **V. Number of Subjects**

1. The anticipated enrollment number is 468 subjects (or 234 for intervention group and 234 for control).
2. The PHQ-9 is widely used, has good internal consistency, is well validated, and is commonly used to inquire about the degree to which an individual has experienced depressed mood over the past two weeks. Our power calculations based on our preliminary work hold the following assumptions: 1) attrition rate of 30% 2) 80% power

3) a two-sided alternative for group differences at the 0.05 level of significance for a change in PHQ-9 scores (average of 4 points, variance of 5.5).

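### Little's MCAR test is not a test of missingness by arm, and a non-significant result cannot show that dropout is unrelated to the intervention

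*Protocol*

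**What the plan says.** The Statistical Assumptions paragraph of the Protocol's Data Analysis Plan (Section VI) states that Little's MCAR test "will be used to test that missingness is in no way related to the intervention". It does not say which variables enter the test, whether arm is one of them, whether the test is run within arms, or what follows from either result.

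The same paragraph sets the handling of missing data: "we will use the Last Observation Carried Forward (LOCF) missing data imputation technique", and then "If the proportion of missing data is higher, we will use regression based multiple imputation". The switch depends on how much is missing, not on Little's test. The next paragraph says that intention-to-treat analysis "will minimize the influence of 'informative missingness' of the data and preserve groups' comparability".

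Section V assumes an "attrition rate of 30"%. The outcome model in the Protocol is a mixed model with a separate intercept and slope for each arm.

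The SAP does not mention Little's test. Its Statistical Assumptions section has a different first-line rule: "we will substitute the mode for categorical data and the median for continuous data", with multiple imputation if more is missing.

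Neither document plans an analysis of dropout by arm or a sensitivity analysis for data missing not at random.

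**The concern.** The test does not match the purpose given to it. Little's test asks whether groups of participants with different missing-data patterns have the same means on what was observed. Dropout can differ sharply between arms while those means stay alike. Failing to reject a null hypothesis also does not prove it, so no outcome of this test supports a statement that missingness and intervention are unrelated. Nor can any test on observed data speak to dropout driven by scores never collected.

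Arm-related dropout is plausible here. Only the intervention arm has the Facebook and photograph tasks, the added one-week technical support call (Section VI) and the follow-up interviews (Section X). With attrition assumed at 30%, a moderate imbalance would involve many participants. Little's test is the only check on missingness that the Protocol names. At stake is a trial report stating, on the strength of a non-significant p-value, that missingness had nothing to do with the intervention.

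**Working it through.** The plan gives no figure for this test, so there is nothing to reproduce. The check asks how often the test would flag differential dropout.

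**Inputs from the Protocol.** 468 caregivers, 234 per arm; five pre-bereavement assessments (baseline, 14, 30, 90 and 150 days); two-sided 0.05; attrition around 30%.

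**Assumptions not in the documents.** Normal PHQ-9 scores with SD 5.5, visit correlation 0.6, monotone dropout, and the dropout splits below. There were 500 simulated trials per setting, so the Monte Carlo standard error is about 1 point at 5% and 2 points at 25% or 66%.

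**Statistic.** d² = Σ n_k (ȳ_k − μ̂_k)′ Σ̂_k⁻¹ (ȳ_k − μ̂_k), summed over missing-data patterns k, with maximum-likelihood mean and covariance. Degrees of freedom are the observed variables summed over patterns, minus the number of variables. Scores only: (1+2+3+4+5) − 5 = 10. With arm added: (2+3+4+5+6) − 6 = 14.

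**Simulated rejection rates at 0.05**

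| Setting (control v intervention dropout) | Little, arm not entered | Little, arm entered | Chi-square of dropout by arm |
|---|---|---|---|
| 30% v 30%, completely at random | 5% | 5% | 4% |
| 25% v 35%, no treatment effect | 5% | 25% | 66% |
| 20% v 40%, no treatment effect | 5% | 91% | 100% |
| 20% v 40%, 4-point effect by last visit | 8% | 91% | 100% |
| About 33% each, dependence on last score opposite by arm | 5% | 6% | 4% |

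A second, independent simulation gave about 4-5% without arm. With arm it put the rejection rate at about 20-25% for 25% v 35% and 91% for 20% v 40%.

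**Check by formula.** The standard error of the difference in dropout is √(2 × 0.30 × 0.70 / 234) = 0.0424.
- 25% v 35%: z = 0.10 / 0.0424 = 2.36; power of the direct comparison = Φ(2.36 − 1.96) = 66%.
- 20% v 40%: z = 0.20 / 0.0424 = 4.72; power = Φ(4.72 − 1.96) = 99.7%.

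With arm entered and unrelated to the scores, Little's statistic carries roughly the same signal, z² = 5.57 or 22.3, but spreads it over 14 degrees of freedom instead of 1. The 5% critical value is 23.7, and the non-central chi-square gives power of about 26% and 89%, in line with the simulation.

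**The last row of the table.** When dropout depends on the previous score in opposite directions in the two arms, the pooled test misses it whether or not arm is entered, and so does the plain comparison of dropout rates. Little's test run separately within each arm (Bonferroni) rejected in 98%. A missingness model therefore needs an arm-by-score interaction.

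**Why LOCF matters here, apart from the test.** Suppose, as an assumption, that both arms change by 4 points over time and dropout differs by 20 percentage points. If dropouts carry forward baseline, the spurious difference is 0.20 × 4 = 0.8 points. If they carry forward a value from halfway, it is 0.20 × 2 = 0.4. A simulation under the same 4-point trend, with dropout related to arm alone, gave about 0.2-0.5.

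**The case against.** The strongest defence is that the sentence speaks of the intervention, so the authors may have meant to enter arm or to run the test within arms. The text does not exclude this. A reader might infer that Little's test cannot detect arm-related dropout at all. The documents do not support that: with arm entered it detects 20% v 40% in about 91% of trials. What stands against the sentence is that the choice is not specified, that even with arm the test is much weaker at 25% v 35%, and that no version turns non-significance into evidence of no relation.

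A reader might also infer that a non-significant result would license LOCF. It would not: the choice between LOCF and multiple imputation rests on the proportion missing, and no step depends on this test.

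A third tempting step is to attach a bias in the completer difference. Neither document plans a completer analysis, so such a figure would not describe this trial.

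Finally, dropout related to arm alone is ignorable for a likelihood mixed model containing arm, which the Protocol already plans. That stands for the mixed model on observed data. It does not protect the LOCF default, and it does not cover dropout that depends on unseen scores. Intention-to-treat does not cover these either, since it cannot supply scores that were never collected.

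**Conclusion.** The point holds. The Protocol gives Little's test a purpose that it does not serve. Unless arm is entered, it has almost no power for differential dropout: about 5% at both 25% v 35% and 20% v 40%, and 8% at the latter with a 4-point effect, against about 66% and over 99% for a direct comparison. With arm entered it remains weaker at 25% v 35% (about 20-25%). Pooled over arms it misses outcome-dependent dropout of opposite direction (5-6%).

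A non-significant result could give false reassurance; it need not, since the test can reject. The rejection rates rest on the assumed splits, SD 5.5, correlation 0.6 and monotone dropout. The logical objection, that non-significance cannot show no relation or address unseen scores, rests on none of these.

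Because no decision depends on the result, the direct harm is an unsupported statement in the report. It should be corrected, but on its own it does not bias the primary estimate.

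**What to change.** 1. Delete the sentence on Little's test from the Protocol. The SAP has no such sentence to remove.
2. Report dropout and its reasons by arm, visit and phase (active caregiving, bereavement).
3. Model missingness on arm, prior PHQ-9 scores and their interaction.
4. Make the Protocol's likelihood mixed model on observed data, or multiple imputation under missing-at-random, the primary analysis in place of LOCF.
5. Pre-specify a missing-not-at-random sensitivity analysis. Delta adjustment, worsening imputed intervention-arm scores until the conclusion changes, is one suitable form.
6. Reconcile the missing-data rules of the two documents: LOCF then multiple imputation in the Protocol, median or mode substitution then multiple imputation in the SAP.

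The cost is wording in both documents and one or two extra tables. No new data collection is needed beyond recording reasons for dropout where this is not already done.

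### Beyond a few fixed terms, covariates enter the outcome models only when a baseline significance test flags them; a short prespecified list should replace this rule

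*Protocol*

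**What the plan says.** The Protocol's Data Analysis Plan (Statistical Assumptions) compares baseline measures and demographics between arms, "using chi-square or t-test analysis for categorical or continuous variables, respectively", and continues: "Variables that differ significantly between groups will be included in regression models as potential confounders". The SAP, under Statistical Assumptions, has the same rule and adds the restriction "Additional confounders will only be introduced as covariates if we find evidence of imbalance between groups at baseline", which the Protocol also carries. Neither document lists the variables to be tested or gives the significance level for these tests.

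Some terms do not depend on the tests:

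- **Protocol, Data Analysis Plan:** hospice agency and time to last observation are always included.
- **SAP, Statistical Analysis:** the displayed model always contains the baseline measure and time since enrollment. It has no term for agency.
- **Protocol, displayed model for H1a and H1b:** arm-specific intercepts and slopes with a random intercept, and no baseline term. The text does not say whether the baseline score is one of the repeated responses.

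The Protocol's Subgroup Analysis paragraph names age, gender, race and ethnicity, relationship to and residence with the patient, and patient comorbidities as possible influences on outcome. Outside the test-based rule, these appear only as subgroups.

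**The concern.** Allocation is computer-generated, so a baseline difference between the arms is a chance event. A p-value for that difference does not show whether the variable predicts PHQ-9, GAD-7 or grief, and prediction is what makes adjustment worthwhile. Selecting on the p-value will usually leave out a variable that matters and will sometimes bring in one that does not. With neither the candidate list nor the threshold written down, nobody can say before seeing the data which model will be reported. At stake are some precision from data the trial will hold anyway, and a primary model that is not fully prespecified.

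**Working it through.** **The plan's own figure.** The plan gives no power figure for adjusted analyses. Its sample-size statement (Protocol, V. Number of Subjects) is 468 in total, 234 per arm, with "attrition rate of 30% 2) 80% power", a two-sided 0.05 level, and a 4-point PHQ-9 change with variance 5.5. Those inputs do not reproduce 468. Variance 5.5 needs 6 per arm, or 18 in total after dividing by 0.70. Reading 5.5 as an SD needs 30 per arm, or 86 in total. That is a separate matter. The check below uses only the number of evaluable caregivers and sets the effect so that an unadjusted comparison has 80% power.

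**Inputs.**
- Evaluable per arm: 234 × 0.70 = 163.8, taken as 164.
- Effect for 80% unadjusted power: (1.960 + 0.842) × √(2/164) = 0.309 SD.
- Level of the balance tests: not stated, so 0.05 is assumed.
- Correlation ρ between covariate and outcome: not stated, so 0.15 to 0.7 is assumed.

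**How often a variable is left out.** Under randomisation a given variable is flagged with probability 0.05 and omitted with probability 0.95. With 10 independent variables (an illustration), the chance that none is flagged is 0.95^10 = 0.60.

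**Size and power in a single-endpoint model.** Let δ = 1.960 + 0.842 = 2.80 under the alternative and 0 under the null. Given a baseline z-value u, the unadjusted outcome z-value is normal with mean δ + ρu and variance 1 − ρ².
- Always adjusting: power ≈ Φ(δ/√(1 − ρ²) − 1.96). For ρ = 0.3 this is Φ(2.80/0.954 − 1.96) = 83.6%.
- Test, then adjust: integrate the unadjusted rejection probability over |u| < 1.96, then add 0.05 × the rejection probability of the adjusted test.

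| Assumed ρ | Size under the rule | Power under the rule | Power, prespecified | Points lost |
|---|---|---|---|---|
| 0.15 | 4.9% | 80.1% | 80.9% | 0.8 |
| 0.2 | 4.9% | 80.2% | 81.6% | 1.4 |
| 0.3 | 4.8% | 80.4% | 83.6% | 3.2 |
| 0.5 | 4.3% | 81.1% | 89.9% | 8.8 |
| 0.7 | 3.6% | 82.0% | 97.5% | 15.5 |

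Simulation with 164 per arm (60,000 null and 20,000 alternative runs per setting) agrees at ρ = 0.3, 0.5 and 0.7. Sizes under the rule are 0.049, 0.044 and 0.037. Powers are 80%, 81% and 81% under the rule, against 83%, 90% and 97% prespecified.

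**The Protocol's slope contrast.** In a random-intercept model with complete data, the standard error of the difference in slopes is √(2σ²/(n·S)). Here σ² is the residual variance and S is the sum of squared deviations of the visit times. The intercept variance, which is what a time-fixed covariate explains, does not appear. For visits at 0, 14, 30, 90 and 150 days in units of 150 days, S = 0.692. With an assumed residual SD of 0.8 times the intercept SD and 164 per arm, the standard error is √(2 × 0.64/(164 × 0.692)) = 0.106, with or without the covariate. In a simulation of this model with random early dropout and a covariate correlated 0.6 with the intercept, it was 0.180 without and 0.178 with the covariate.

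**H2.** Protocol Table 2 describes TRIG-Present as a measure for bereaved people. The first grief score therefore follows the patient's death, and so follows randomisation. The SAP model's baseline-measure term has no enrolment value to use for grief. Yet the Protocol's Research Objectives/Background section says that pre-bereavement depression and anxiety go with more intense grief. Baseline PHQ-9 and GAD-7 are thus prognostic by the documents' own account, but they enter the H2 model only if a balance test flags them.

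**The case against.** The best defence is that the plan is less exposed than the rule suggests. The Protocol already fixes agency and time to last observation, and the SAP model fixes the baseline score, probably the strongest single predictor of a later PHQ-9 or GAD-7 score. What remains under the rule is mainly age, gender, relationship and residence. Their correlations with outcome after baseline adjustment are unknown and may be modest, so the loss may be about 1 point of power. For the Protocol's slope contrast it is close to nil. All of this stands, and it limits the size of the point.

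It does not remove the point. The Protocol's displayed model has no baseline term, the SAP model has no agency term, and H2 has no enrolment baseline. The remaining covariates are still chosen after the data are seen.

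Three stronger readings are tempting, and the documents do not support them:
- *No covariate enters without a flagged imbalance.* The fixed terms listed above contradict this.
- *The rule inflates false positives.* The size is below 5% at every assumed correlation above.
- *The primary analysis loses 9 points of power or more.* That needs a correlation of 0.5 or higher. Such a value best fits the baseline score, which the SAP already includes, and the figure does not carry over to the slope contrast.

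**Conclusion.** The concern holds in limited form. For every covariate outside the fixed terms, selection by baseline significance test omits a given prognostic variable about 95% of the time, can admit irrelevant ones, and leaves the model open until the data are in. The shift in test size is small and conservative. In a last-observation model the power cost is about 1 point at correlations of 0.15 to 0.2, 3 points at 0.3 and 9 points at 0.5. For a main-effect covariate in the Protocol's slope contrast it is little or nothing. H2 has the most to gain, provided that baseline distress predicts grief as the Protocol says.

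These sizes rest on an assumed 0.05 level for the balance tests, assumed correlations, one normal covariate and one post-baseline value. They ignore the clustering of caregivers of the same patient, who share an allocation. The argument for prespecification does not depend on those assumptions. The rule does not invalidate the trial, but it should be changed.

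**What to change.** 1. Delete the test-then-adjust sentences from the Statistical Assumptions text of both the Protocol and the SAP.
2. Put one short covariate list in both documents, used whatever the observed imbalance: hospice agency; the baseline value of the outcome where one exists; caregiver age and sex; and relationship to and residence with the patient.
3. State how the baseline score enters (as a covariate or as a repeated response), and make the Protocol and SAP models agree.
4. For H2, use baseline PHQ-9 and GAD-7 in place of the missing grief baseline.
5. Present the baseline table without p-values.

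The cost is a wording change and a few degrees of freedom. The planned balance tests and subgroup analyses already call for baseline measures and caregiver characteristics of this kind.
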